
KEY PERSONNEL (List names of all investigators including PI and their respective specialties)

Name	Professional Discipline/ Specialty	Role in the Project
1. [name]	Environmental Microbiologist	PI
2. [name]	Sustainable Development Specialist	Co-PI
3. [name]	Environmental Health Specialist	Co- PI
4. [name]	Epidemiologist	Co-I
5. [name]	Microbiologist	Co-I

DESCRIPTION OF THE RESEARCH PROJECT

Hypothesis to be tested:

Concisely list in order, in the space provided, the hypothesis to be tested and the Specific Aims of the proposed study. Provide the scientific basis of the hypothesis, critically examining the observations leading to the formulation of the hypothesis.

We postulate that the ecology of *Vibrio cholerae* O1 in Mozambique will be similar to Bangladesh and similar environmental intervention may be applicable to reduce the incidence of cholera in Mozambique.

Specific Aims:

Describe the specific aims of the proposed study. State the specific parameters, biological functions/ rates/ processes that will be assessed by specific methods (TYPE WITHIN LIMITS).

- 1) Transfer of technology from ICDDR,B laboratories in Bangladesh to the Center for Environmental Hygiene and Medical Exams (CHAEM) at Beira of Mozambique.
- 2) To find out the role of phytoplankton and zooplankton as habitat of *V. cholerae* in the aquatic environment of Mozambique
- 3) To see the role of various physicochemical parameters in multiplication of *V. cholerae* O1 in the aquatic environment of Bangladesh and Mozambique.
- 4) To find out intervention strategies to reduce cholera incidence at Beira, Mozambique.

Background of the Project including Preliminary Observations

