Fig. 4. Attachment of *V. cholerae* O1 in caudal setae of copepod (*Mesocyclops* sp.) is shown. Arrow shows *V. cholerae* O1. Original magnification X 400.

Similarly it was also found that *V. cholerae* secretes an enzyme mucinase (Schneider *et al.*, 1982) and the role of the mucinase is to degrade the mucin from the environment. The mucin is present in the plant cell wall therefore it was thought that *V. cholerae* can also make an association with the aquatic plant (Islam and Aziz, 1981). Studies have shown that various aquatic plants e.g. water hyacinth, marine algae, duck weeds, green algae can act as temporary reservoirs of *V. cholerae* O1 in the aquatic environment (Spira *et al.*, 1981; Islam *et al.*, 1988, 1989, 1990b). However, finally it was found by both laboratory and field based studies that a blue green alga, *Anabaena* spp. can act as a long term reservoir of *V. cholerae* O1 in the aquatic environment (Islam *et al.*, 1990a, 1994a). Fig. 5 shows *V. cholerae* O1 inside the mucilaginous sheath of *Anabaena variabilis*.

The months of cholera seasons in Mozambique has a correlation with rainfall ($p < 0.001$) (Fig. 6) which is different from the cholera seasons in Bangladesh (Fig. 7). In Bangladesh, cholera epidemics have two peaks, the highest peak during post monsoon and a second small peak during pre-monsoon. This difference in seasonality of cholera epidemics needs to be investigated from ecological point of view. It is not known during rainy season what changes take place in various parameters of water (eg. pH, salinity, conductivity etc.) which may be favorable for multiplication of bacteria in the aquatic environment in Mozambique.

[figure not shown]

Fig. 5. Phase-contrast microscopy showing *V. cholerae* O1 inside the mucilaginous sheath of a blue green alga, *Anabaena variabilis*. Arrows show a filament of *Anabaena variabilis*. Original magnification X 630.

There is no information about the occurrence of phytoplankton and zooplankton in the aquatic environment in Mozambique during epidemic seasons. Therefore the present study aims at investigating the possible environmental factors responsible for different epidemiological pattern of cholera in Mozambique and Bangladesh.

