The sampling at Beira, Mozambique for the analysis of cholera ecology will include the sea, river, well water, and other surface water bodies. Basic water chemistry tests at sites will include conductivity, pH, temperature, salinity, dissolved oxygen and total dissolved solids. In the laboratory we will analyze free carbon dioxide, chlorides and hardness. Tests for *V. cholerae* will include culture by enrichment technique to (qualitative) assess the presence of vibrios in water, phytoplankton and zooplankton. Faecal coliforms in water will be counted by the membrane filtration technique; fluorescent microscopy will indicate the non-culturable vibrios, alive or dead. Colony blots will provide the detailed quantitative assessment of vibrios in the sample. All of these tests will be carried out every 15-day interval throughout the study. The CHAEM laboratory at Beira has been selected as the main base for developing capacity and for carrying out some of the microbiological analysis for this research. Procedures will be set up as part of the future monitoring system. In course of time, the more routine laboratory procedures will also eventually be enhanced at Quelimane and Maputo. Equipment for chemical and microbiological testing used in this research will remain with the centre at Beira after completion of the project.

Phase II: Like Bangladesh, if it is found in the first phase of the study that phytoplankton and zooplankton are also acting as reservoirs of cholera in Mozambique, then environmental cholera intervention strategy will be introduced using capulanas as a filtering device in the second phase. The intervention study will be carried out in two phases. The first phase study will be in-depth laboratory-based investigation to find out the effectiveness of capulanas to remove phytoplankton and zooplankton associated *V. cholerae* O1 and O139. In the second phase, acceptability and effectiveness of capulanas will be investigated in the community to reduce cholera incidence.

After successful completion of the first phase, which includes the identification of risk factors of cholera and its environmental intervention, attempts will be made in the second phase to focus on the identification of the risk factors for other infectious diseases in Mozambique particularly for Shigellosis.

Environmental monitoring

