All the environmental samples will be processed in the Environmental Microbiology Laboratory in Dhaka. All the techniques required for testing the environmental samples are already in place in this laboratory with adequate manpower and expertise. All the equipments are also available in this laboratory.

Data Analysis

Describe plans for data analysis. Indicate whether data will be analyzed by the investigators themselves or by other professionals. Specify what statistical software packages will be used and if the study is blinded, when the code will be opened. For clinical trials, indicate if interim data analysis will be required to monitor further progress of the study. (TYPE WITHIN THE PROVIDED SPACE).

The isolation and enumeration of *V. cholerae* O1 and O139 from various environmental samples by culture, FA, and colony blot hybridization will be related with the physicochemical parameters of water and the seasonality of cholera. The data from Bangladesh will be compared with the data from Mozambique to find out the role of environmental factors in the seasonality and endemicity of cholera in these two countries.

Logistic regression analysis will be done to do the qualitative analysis (i.e., the presence and absence of *V. cholerae* O1 and O139 using culture technique). For quantitative analysis, Poisson regression analysis will be used.

The biweekly data from both the lotic and lentic environment will be analyzed by first computing the percentage of samples positive by FA, conventional culture and colony blot hybridization by site combination using McNemar test (Sokal and Rohlf, 1989).

A two-way analysis of variance will be performed with site and month as the effects in the model and model assumptions will be determined by examining residuals for normality following the procedures described by Sokal and Rohlf (1989).

The correlation of association between phytoplankton and zooplankton with *V. cholerae* will be analyzed using Pearson's correlation method.

Ethical Assurance for Protection of Human Rights

Describe in the space provided the justifications for conducting this research in human subjects. If the study needs observations on sick individuals, provide sufficient reasons for using them. Indicate how subject's rights are protected and if there is any benefit or risk to each subject of the study.

No human subject is involved in this environmental study.

Use of Animals

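### Aim 3 concerns multiplication of V. cholerae O1, but the planned regressions model concurrent presence and counts, so growth could not be told apart from runoff or faecal input

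*Protocol*

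**What the plan says.** Specific Aims, aim 3: "To see the role of various physicochemical parameters in multiplication of *V. cholerae* O1 in the aquatic environment of Bangladesh and Mozambique". The Background section has the same target in view when it asks about rainy-season changes in water "which may be favorable for multiplication of bacteria in the aquatic environment in Mozambique".

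The Data Analysis section says that isolation and enumeration results "will be related with the physicochemical parameters of water and the seasonality of cholera". It gives two model families: "Logistic regression analysis will be done to do the qualitative analysis" for culture presence or absence, and "For quantitative analysis, Poisson regression analysis will be used". The counts come from the colony blots: Methods states that "Colony blots will provide the detailed quantitative assessment of vibrios in the sample".

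Sampling is every 15 days for three years, and pH, salinity, conductivity and the other field readings are taken at the time of collection. Two possible markers of input are also planned. For Beira, Methods says "Faecal coliforms in water will be counted by the membrane filtration technique" on the same 15-day schedule. For Bangladesh, the section on physicochemical parameters obtains rainfall from the national meteorological service. Data Analysis gives neither marker a role.

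**The concern.** Multiplication is a rate. A count at one visit is a stock: what has washed in, plus what has grown, less what has been diluted or has died. Regressing the stock on chemistry read at the same moment estimates association with concentration, and that equals a growth effect only if input and loss are unrelated to the chemistry.

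Beira is where this is least safe. The Background section reports that the cholera months in Mozambique correlate with rainfall (p < 0.001) and that low-lying parts of Beira flood in the rains. If a rain event brings in contaminated water and also lowers salinity, salinity will be associated with V. cholerae with no effect on growth. A real growth effect in the opposite direction could be masked.

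The comparison of the two countries is at stake. The study hypothesis is that the ecology is similar in both, and a parameter that marks runoff in one country and growth in the other would give a misleading answer.

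**Working it through.** **1. Does any planned measurement isolate growth?** No. The outcome is one presence result or count per sample per visit, with concurrent chemistry. There is no lagged exposure, no modelled change between visits and no microcosm experiment. The one-off denser sampling (ten consecutive days, then weekly for a month) is there to describe variation in pathogen load.

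**2. The plan's own numbers.** Environmental monitoring gives 26 samples a year × 2 sites × 3 years = 156 per sample type at Matlab, and 156 × 3 = 468 in all. Both reproduce. One site over three years gives 26 × 3 = 78 visits.

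**3. Positivity in the protocol.** Table 1 (Bangladesh, culture) has 21/1923 = 1.1% of water samples and 12/1923 = 0.6% of each plankton type positive. At 1.1%, 78 visits yield 78 × 21/1923 = 0.85 positives, and 156 yield 1.7.

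**4. Simulation at one site, 78 visits, no growth effect.** Every coefficient is assumed; none comes from the protocol.
- salinity = −0.8 season − 0.7 rain + noise (SD 0.7)
- log input = 0.8 season + 0.6 rain + noise (SD 0.5)
- measured log coliforms = log input + error (SD s)
- count ~ Poisson(exp(a + log input + g × salinity) × gamma with shape 2 and mean 1), with g = 0

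The test is the 5% test on salinity in a Poisson model. With a = 0.7 the mean count is about 3.1 and 71% of samples are positive. Lowering only a, with s = 0.3, gives:

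| Samples positive | Salinity alone | Plus annual sine and cosine |
|---|---|---|
| 71% | 97% | 79% |
| 16% | 54–57% | 29–31% |
| 3% | 10% | 9% |
| 1.1% | 2% | 3% |

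The first two rows use a dispersion correction; in the last two the scale is fixed at 1. In the last row 77% of runs had fewer than two positives and were counted as non-rejections.

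At 71% positive, when rain moves salinity but not input, season-adjusted rejection is about 9%. Most of the 79% is therefore confounding by rain events rather than a miscalibrated test. With a weaker rain effect on input (0.3), the season-adjusted figure is 37%.

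**5. What coliform adjustment does (71% positive, season terms kept).** Rejection falls to 13% at s = 0, 16% at 0.3, 28% at 0.5 and 46% at 0.8. The 13% with error-free measurement partly reflects small-sample behaviour of the dispersion-corrected test. With a true growth effect of g = +0.4, power is 9% with season terms only and 63% with coliforms added.

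**6. What rainfall adjustment does.** In a second simulation, 156 Poisson counts depend only on rain (log-rate slope 0.5 per SD), and salinity has correlation −ρ with rain. A faecal marker has correlation 0.8 with rain.

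| ρ | Mean count | Salinity alone | Plus faecal marker | Plus rain |
|---|---|---|---|---|
| 0 | 1 | 9.5% | 7% | 6.5% |
| 0.3 | 1 | 45% | 10% | 4.7% |
| 0.5 | 1 | 83% | 23% | 5.2% |
| 0.5 | 5 | 100% | 74% | 5.2% |
| 0.7 | 1 | 98% | 46% | 5.6% |

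The excess at ρ = 0 is overdispersion, not confounding. Rainfall restores about 5% because it is the true driver by construction, so this is the favourable case.

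**The case against.** The strongest reply is that this is a mismatch of wording. The protocol states no null hypothesis for aim 3 and does not say how a coefficient will be interpreted, and covariates can be left to an analysis plan. That largely stands. A reader might infer that the study would report runoff as a growth effect, or that coliforms are excluded from the models. The text supports neither; silence on a covariate is not exclusion. Two things remain. The Background section itself argues that favourable water conditions lead to multiplication and so to heavy contamination. And in the appended correspondence the investigators tell the review committee that Data Analysis holds the detailed plan. The fault is that the stated outcome cannot answer the stated aim, whatever the covariate list.

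The mechanism is also less documented than it may seem. The Background says that the rainy-season changes in water chemistry are unknown, so a fall in salinity is an assumption. Its remark on human passage concerns a lowered infectious dose, not the load in water, and cannot support the input path. The rainfall correlation is with cholera months, not with V. cholerae in water.

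The large percentages need frequent positives. This stands: at Table 1 yields they vanish. Table 1 is Bangladeshi culture data, however, and colony-blot or Beira yields may differ.

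Finally, a runoff marker may still predict epidemics. That is fair, so harm to the early-warning output is not shown. The harm is to the claim about growth and to the comparison between countries.

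**Conclusion.** The point holds as a mismatch between aim and estimand. The logistic and Poisson models can show association of water chemistry with occurrence and concentration of V. cholerae; they cannot separate multiplication from input, dilution and die-off.

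The size is conditional. Given that rain lowers salinity and raises input as assumed, season-adjusted false rejection for salinity is about 80% at 71% positive, about 31% at 16% positive, and near or below nominal at about 1% positive. The low figure at 1% is no reassurance, because most such runs hold too few positives to test anything. None of these values forecasts this study's error rate. They show that season terms and a dispersion correction do not remove the ambiguity once positives are common enough to analyse.

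**What to change.** - In Specific Aims (and where the project summary repeats aim 3) and in Data Analysis, state the aim 3 conclusion as association with occurrence and concentration of V. cholerae O1, not with its multiplication.
- Report each physicochemical coefficient with and without adjustment for markers of input. Use rainfall in both countries: it is already obtained for Bangladesh, and a source for Beira has to be named.
- Use the same adjustment set in both countries for the comparison. Add log faecal coliform count as a further Beira analysis only, since coliforms are not listed in the Matlab procedures.
- Do not adjust for stool-positive cases. They may be a consequence of contaminated water, and conditioning on them could remove or distort the association sought.
- Do not treat a coefficient that persists after adjustment as proof of a growth effect.

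The cost is a change of wording, one rainfall source for Beira and a few extra model fits. The aim 3 conclusion becomes more modest, and some confounding remains because coliforms track V. cholerae input imperfectly.

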The project is an interdisciplinary and collaborative activity between three institutions that in the first instance focuses on the development of cholera monitoring and prediction in Mozambique. This is based on the consolidation of earlier research findings from a wide variety of sources including those based on Mozambique and Bangladesh through the recognized studies of those coordinating this proposal. The initial phase of the project focuses on testing the hypothesis that environmental influences on cholera ecology are similar in Mozambique to those in Bangladesh. This necessitates transfer of technology from Dhaka to Beira, for microbiological monitoring of cholera epidemic, and comparison with studies in Bangladesh. The collaboration requires capacity building in the Mozambique laboratories to streamline some existing procedures and to introduce new ways of monitoring *V. cholerae* from the environment and from the people who become cholera patients. The specific techniques for the microbiological analysis will include the following: culturing of diarrhoeagenic pathogens, monitoring of standard water quality indicators as well as physicochemical parameters of the water samples, further work on preserved samples, analysis of phytoplankton and zooplankton in selected water bodies, and the use of specific detection technologies such as fluorescent antibody technique and colony blot hybridization technique. In Bangladesh, we will carry out environmental surveillance of one pond and river in Matlab and the clinical data will be obtained from the hospital records of Matlab. This environmental and clinical surveillance will be carried out to have a comparative data of cholera endemic areas of Bangladesh and Mozambique.

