chamber, and will be incubated at 37°C for 30 ± 5 minutes protecting from light. Then the slides will be rinsed thoroughly with PBS protecting from light. Excess moisture will be absorbed using a blotting paper. A drop of fluorescent mounting medium will be added on the slide and covered with a 22 x50mm, No. 1 cover slip. For best results, the slides will be read immediately at a magnification of 1000 X with oil immersion. The slides will, however, be kept cool, in the dark, or will be kept humid to prevent drying.

Colony blot hybridization technique

Preparation of colony blots and hybridization will be carried out according to published procedures (Wright *et al.* 1992 and Maniates *et al.* 1982). Environmental water samples will be plated directly or upon appropriate 10 fold serial dilutions on non selective LB agar plates and incubated overnight at 37°C. Colonies will be transferred to a Whatman # 541 filter paper from the culture plates. The filters will be transferred with colony side up on to # 3 Whatman filters that are pre-soaked with denaturation solution (4 ml) for 10 minutes. The filter paper will be saturated with neutralizing solution (4 ml) for 3 min then the filter will be air dried and soaked in pre hybridization buffer at 42°C for 1 hour. Then hybridization will be carried out with DIG labelled ctx probe at 42°C for over night. Then the washing, blocking and signal detection will be carried out following the procedures provided by the manufacturers (Boehringer Mannheim, Japan).

Physicochemical parameters of water

Physicochemical measurement will be made at the time of collection at each sampling site. This will include water temperature, pH (Orion Portable pH Meter, Cat. No. 210 A, Orion Research, USA), salinity, total dissolved solids and conductivity (HACH Conductivity Meter, Cat. No. 51800-18, Sension™ 5, HACH Company, USA) and dissolved oxygen content (HACH Dissolved Oxygen Meter, Cat. No. 51850-18, Sension™ 6, HACH Company, USA). All these readings will be taken in the field using potable meters. The free CO₂, hardness and chloride will be measured in the laboratory following standard procedures (APHA, 1998). The number of hours of sunshine, total rainfall and the ambient temperature will be obtained from the Metrological Department of Bangladesh in Dhaka.

Clinical surveillance

Data on the incidence of cholera in Matlab, Bangladesh will be collected from the Matlab Hospital records of ICDDR,B.

Activities in Mozambique:

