Like Bangladesh, environmental samples will be collected from both lotic (open water, e.g., river, canal, sea etc.) and lentic (closed water, e.g., pond, lake, wells etc.) environment of Beira, Mozambique. Phytoplankton, zooplankton and water samples will be collected every two weeks interval. The samples will be transported to the CHAEM laboratory following standard procedures and processed following the same procedures as described in Bangladesh part. The isolation and identification of *V. cholerae* O1 and O139 will be carried out following enrichment technique as described in material and methods section in Bangladesh part. The VBNC *V. cholerae* O1 and O139 will also be detected using direct fluorescent antibody technique. All these methodologies will be set up in CHAEM laboratory by ICDDR,B as a part of technology transfer. Samples will be processed and preserved for detection of *V. cholerae* O1 and O139 by colony blot hybridization from the environmental samples. Preparation of colony blots will also be carried out in CHAEM and the dried blots will be sent to ICDDR,B for hybridization using DIG labelled probe.

The stool sample from the patients having watery diarrhoea from Infectious Diseases Hospital in Beira will be tested by dark field microscope as well as by using culture technique at CHAEM. The information about the patient will be taken from the record of Infectious Diseases Hospital.

The phytoplankton, zooplankton and chemical analysis will be carried out at CHAEM in Beira following the methods described in Bangladesh part.

Facilities Available

Describe the availability of physical facilities at the place where the study will be carried out. For clinical and laboratory-based studies, indicate the provision of hospital and other types of patient's care facilities and adequate laboratory support. Point out the laboratory facilities and major equipment that will be required for the study. For field studies, describe the field area including its size, population, and means of communications. (TYPE WITHIN THE PROVIDED SPACE).

The sampling sites will be selected at Matlab, a field study area of ICDDR, B located 70 km southeast of Dhaka in a low lying deltaic region. All the cholera patients from the sampling sites will be reported to the hospital for treatment. We will be able to know the time of cholera epidemic from the hospital records.

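### Phase I asks whether environmental influences on V. cholerae are alike in two countries, but the listed analyses name no country contrast, no site-by-month term and no weather source for Beira

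*Protocol*

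**What the plan says.** The section on the hypothesis postulates that the ecology of V. cholerae "O1 in Mozambique will be similar to Bangladesh and similar environmental intervention may be applicable to reduce the incidence of cholera in Mozambique". The Methods section describes the initial phase as "testing the hypothesis that environmental influences on cholera ecology are similar in Mozambique to those in Bangladesh".

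The Data Analysis section gives the comparison as an intention: "The data from Bangladesh will be compared with the data from Mozambique to find out the role of environmental factors". It then lists logistic regression for presence or absence, Poisson regression for counts, McNemar tests between detection methods, Pearson correlation of plankton with V. cholerae, and this: "A two-way analysis of variance will be performed with site and month as the effects in the model". It names no country term, no interaction and no criterion for similarity.

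The Background ties the Mozambican season to rainfall (p<0.001), "which is different from the cholera seasons in Bangladesh", where there are two peaks a year. Under Physicochemical parameters of water, sunshine hours, "total rainfall and the ambient temperature will be obtained from the Metrological Department of Bangladesh in Dhaka". Neither the Beira test list in Methods nor Activities in Mozambique mentions weather data.

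Matlab contributes one pond and one river. At Beira the lotic class is "open water, e.g., river, canal, sea etc", and the lentic class includes wells.

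**The concern.** Whether an environmental influence is similar in two countries is a question about a country-by-factor effect: does the association with rainfall, pH or salinity differ between Beira and Matlab? The listed methods describe associations or differences between sites, months or detection methods. None, as specified, estimates that quantity.

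Three features make the gap matter:

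- **Season.** A model with one shared monthly profile cannot describe two places whose seasons are said to differ.
- **Rainfall.** Its effect cannot be compared between countries if the series is collected for only one of them.
- **Water type.** A country contrast that sets a pond and a river against a mix including sea and wells confounds country with water type and salinity, and salinity is itself under study.

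At stake is what the study can say about which environmental variables carry over from one country to the other, which the Background gives as the purpose of the comparison.

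**Working it through.** **1. The plan's own figure.** Environmental monitoring gives 26 samples a year × 2 water systems × 3 years = 156 per component, and 156 × 3 components = 468. Both reproduce. The stated purpose of this size is a two-log reduction in counts at each site, not a between-country comparison. The number of Beira sites is not stated.

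**2. Season in a main-effects ANOVA.** Let two sites have seasonal profiles s₁(j) and s₂(j), each averaging zero over the year. A site + month fit estimates (s₁+s₂)/2 for month j and leaves ±(s₁−s₂)/2 in the residual. With opposite profiles ±A·cos(2πj/12), the fitted month effect is zero and the mean square left over is A²/2.

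Take 2 sites × 12 months × 2 samples × 3 years = 144 observations, 13 parameters, 131 residual degrees of freedom and error variance 1. The expected residual mean square is then:
- A = 1: 1 + 144×0.5/131 = 1.55
- A = 0.5: 1 + 144×0.125/131 = 1.14

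Share of 300 simulated data sets with p<0.05 (one site per country; amplitudes and profiles assumed):

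| Profiles | Amplitude | Site (main effects) | Month (main effects) | Site-by-month |
|---|---|---|---|---|
| Opposite | 0.5 SD | 4% | 2% | 81% |
| Opposite | 1 SD | 1% | 0% | 100% |
| Two peaks v one | 0.5 SD | 3% | 34% | 46% |
| Two peaks v one | 1 SD | 2% | 94% | 99.7% |

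Two peaks against one is closer to what the Background describes for Bangladesh. There the main-effects model often flags month, but the profile it estimates is an average that fits neither place. Only the interaction shows that the seasons differ.

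**3. Weather, side by side.** The Background relates cholera months to rainfall in Mozambique. The weather series are to come from the Bangladesh service. Activities in Mozambique carries over the Bangladesh procedures for samples and for plankton and chemical analysis, not for meteorology. A country-by-rainfall term needs rainfall from both places.

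**4. Precision by culture.** Table 1 gives 21/1923 = 1.09% for water and 12/1923 = 0.62% for each plankton type. Expected positives in 156 samples are 156 × 21/1923 = 1.70 and 156 × 12/1923 = 0.97.

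Assume 156 independent samples per country. The large-sample SE of a crude log odds ratio, with equal rates, is:
- Water: √[2(1/1.70 + 1/154.30)] = 1.09. The 95% CI around 1 is e^(±1.96×1.09), about 0.12 to 8.5.
- Plankton: √[2(1/0.97 + 1/155.03)] = 1.44, or about 0.06 to 17.

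These are rough at such small counts. Exact power of Fisher's test (two-sided 5%, assumed) agrees:

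| True ratio | Water | Plankton |
|---|---|---|
| 3-fold | 13% | 3% |
| 5-fold | 47% | 18% |

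With four Beira sites (312 samples), 5-fold power rises to 67% for water and just over 30% for plankton.

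**5. Could a fixed margin be met?** For a 95% CI around 1 to lie within a 2-fold odds ratio for water, n = 2/[(ln 2/1.96)² × 0.0109 × 0.9891] ≈ 1,480 per country, about 16 positives each. The plan has 156 at Matlab.

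**The case against.** The strongest reply is that much is left open rather than fixed wrongly. The ANOVA sentence does not say additive, and replicate samples within months make an interaction estimable. Nor does it say that countries are pooled: the preceding paragraph concerns lotic and lentic waters, so site may mean water system within a country, and then nothing averages out between countries. The logistic and Poisson models could carry country terms, and a separate analysis plan may name them. All of this stands, so it would be wrong to say that the methods cannot test the hypothesis. But in its response to the Research Review Committee (item e) the sponsor presents the Data Analysis section as the detailed plan, and that section leaves the central comparison without a model.

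Four stronger readings are tempting and not supported:

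- **Non-significance will be taken as similarity.** No section says so. It is a risk left by the missing contrast.
- **Beira has no weather data.** Only a named source is missing. Mozambican rainfall has already been related to cholera (Background, Fig. 6), and water temperature, pH and salinity will be measured at Beira.
- **The seasons are opposite.** The Background says different.
- **Phase II rests on this test.** It starts if plankton are found to act as reservoirs in Mozambique, and laboratory work on the filter comes before community use.

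The power figures are also open to challenge. Crude culture prevalence is not the hypothesis, Fisher's test is not in the plan, and DFA and colony blot may give more positives. The figures illustrate precision only.

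**Conclusion.** The point holds in a limited form. The Phase I question is a between-country comparison of environmental influences, and the listed analyses do not, as specified, address it: no country-by-factor term, no site-by-month term despite differing seasons, and a weather source for one country only.

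The cost depends on how the plan is carried out. If the ANOVA spans both countries with main effects only, seasonal differences go into the residual (mean square 1.55 instead of 1 for opposite seasons of 1 SD) and the site and month tests may miss them. If it is run within each country, that loss does not arise, but no country contrast remains. The rainfall effect cannot be compared unless a Beira series is obtained.

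Culture data will be weak in any case, at about 1.7 positive water samples and 1.0 per plankton type in 156. This assumes Table 1 rates and independent samples; serial samples from one pond and one river would carry less information.

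**What to change.** 1. Add site-by-month terms to the ANOVA, or country-specific seasonal terms such as month within country or harmonics with their own phase.
2. Put country-by-covariate terms in the logistic and Poisson models. Report the between-country ratio of effects with its 95% CI, and state that a non-significant difference will not be read as similarity.
3. Obtain the same rainfall, sunshine and air-temperature series for Beira as for Bangladesh.
4. Base the country contrast on matched water types (pond with pond, river with river), with sea and wells as separate strata.
5. Include DFA and colony-blot results in the contrasts.

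The cost is analysis wording and one routine data request. Even so, culture-based contrasts will be imprecise and probably inconclusive, and the plan should say so. A fixed equivalence margin is optional; a 2-fold margin is out of reach for culture at this sample size.
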